#### 11.1.2. Operating characteristics

The following table (Table 2) shows the operating characteristics of the proposed design for this trial with 6 scenarios defined by different DLT rates for 6 dose levels. These operating characteristics are based on 1000 simulations of the trial using the acceptable toxicity range [0.21, 0.39]. The operating characteristics show that the design selects the true MTD with high probabilities and allocate more patients to the dose levels with the DLT rate close to 0.3.

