### **Study design**

This study employs the modified accelerated titration design (ATD) 2A[1] and Bayesian optimal interval design (BOIN) to assign patients in the study cohort and identify MTD.

ATD 2A design assumes that the toxicities and effects increase monotonically with doses. It starts with a rapid initial escalation phase by using cohorts of a single new patient to lower the probability of exposing patients to sub-therapeutic doses.[1] When moderate-to-severe toxicities emerge at higher doses, the acceleration phase ends and the study returns to cohorts with 3 new patients.

The BOIN design is a novel adaptive dose-finding method that allows dose escalation and de-escalation and estimates the posterior probability of toxicity rate using updated information [2]. This design is considered to have higher probability of identifying the MTD.

**Dose levels and sample size:** 250, 500, 750, 900, 1200, 1500 mg (flat dose, with no adjustment of body weight or body surface area)[3]. A maximum of 30 patients will be enrolled in the phase 1 study. Patients who withdraw from the study during the first cycle due to reasons not related to treatment-emergent toxicities will be replaced.

Dose escalation sequence is modified from the Fibonacci sequence.

**Determination of starting dose and its dose levels:** the starting dose is **500** mg (flat dose), which is at dose level 2 and approximately equal to 1/6 of human equivalent dose of highest non-severely toxic dose (HNSTD) in the *cynomolgus* study[4].

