**Target toxicity rate: 30%**

**Study cycle: Every four weeks.**

**ATD phase and cohort size**

The accelerated phase starts with one new patient per cohort. When the patient does not experience dose-limiting toxicities (defined later) during the first cycle of treatment at the assigned dose level, the next new patient will be assigned to the next higher dose level of HLX06 (*ie. intrapatient dose escalation is NOT allowed*).

When the first instance of first-cycle dose-limiting toxicities (DLTs), or the second instance of first-cycle grade $\geq 2$  toxicities of any types occurs, the acceleration phase stops and the cohort expands to **three** new patients at the current and subsequent dose levels and switch to BOIN design.

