##### **3.1.1. Accelerated titration design and cohort size**

In the ATD 2A design, the study starts with acceleration phase. In this phase, each cohort consists of one NEW patient for each dose level. After first cycle of treatment, the patient will be evaluated for the toxicities in last cycle. If this patient does not have DLTs, the next patient is allowed to receive the treatment at the next higher dose level.

In the acceleration phase, the newly enrolled patients start at the highest dose level, in which no moderate toxicities are observed in prior patients.

When the first instance of first-cycle DLT or the second instance of first-cycle grade $\geq 2$  toxicities of any types occurs, acceleration phase ends and the cohorts for the current dose level expand to three NEW patients and the study switches the BOIN design phase.

In the acceleration phase, intra-patient dose escalation is NOT allowed.

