##### **3.1.2. Bayesian optimal interval design and rules of dose escalation and de-escalation**

After the acceleration phase, the study uses BOIN design to determine rule of dose escalation and de-escalation. First, the target toxicity rate in this study is set at **30%**, which is the most

common toxicity rate for conventional 3+3 design, indicating that for an oncologic agent, the toxicity rate higher than 30% is NOT desirable[15].

Different from the rule-based 3+3 design, the decision to escalate or de-escalate in BOPIN design is based on the posterior probability of DLTs from updated information. The probability of DLTs is determined by the number of DLTs and the cumulative number of patients treated at the current dose. The safety boundary to escalate the dose is set at 70% of target toxicity rate (i.e. 21%); and the toxicity boundary is, at 130% of target toxicity rate (i.e. 39%), respectively. If the probability of DLTs at the current dose level falls below 21%, the dose in the next cohort escalates to the next higher level. By contrast, when the probability of DLT at the current dose level arises above 39% (130% of target rate), the dose in the next cohort de-escalates to the next lower level. The dose level for the next cohort remains the same if the probability of toxicity is within the safety and toxicity boundary. The enrollment continues until the maximum of 30 patients are reached.

The detailed rule of dose escalation and de-escalation is tabulated in Table 1.

There are also two pre-set EARLY STOPPING RULES in this study.

- Stop the trial if the lowest dose (dose level 1) is eliminated due to overt toxicities.
- Stop the trial and estimate the MTD if the number of new patients treated at the current dose level reaches 15

The detailed statistical methods for dose escalation and de-escalation and estimation of MTD are described in Section 11. This study uses R software and BOPIN package for setting up the specifications. The detailed R codes for this study are described in the Appendix (Section 15.5).

Patients who experience DLTs may be allowed to continue the treatment at the next lower dose level after the toxicities revert to grade $\leq 1$  in 28 days after last infusion, if the Investigator judges that the patient still meet the inclusion criteria and might benefit from continuous treatment.

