## 11. DESCRIPTION OF STATISTICAL METHODS

### 11.1. Bayesian optimal interval design and sample size determination

We will employ the Bayesian optimal interval (BOIN) design (Liu and Yuan, 2015) to find the MTD. The BOIN design is a novel Bayesian dose-finding method that optimizes patient ethics by minimizing the chance of exposing patients to sub-therapeutic and overly toxic doses. The BOIN design yields an average performance comparable to that of the continual reassessment method (CRM) in terms of selecting the MTD, but has a lower risk of assigning patients to sub-therapeutic or overly toxic doses (i.e., better patient ethics).

The target toxicity rate for the MTD is 0.3 and the maximum sample size is 30. We will enroll and treat patients in cohorts of size 3. But in this study, there are two early stopping rules: (1) when the lowest dose level is eliminated due to toxicity and (2) when the new patient number at certain dose level reaches 15.

The dose escalation/de-escalation rules have been described in the Synopsis and tabulated in Table 1. The R codes used in the BOIN 2.4 package to derive the rules are listed in Section 15.5.

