**Table 2 Operating Characteristics of the BOIN design**

Toxicity range	Dose level						Number of pts	% early stopping
	1	2	3	4	5	6		
[0.21, 0.39]	True DLT rate	0.05	0.10	0.30	0.45	0.60	0.8	
	Selection %	0.3	18.9	58.5	20.0	2.3	0	27.7
	# pts treated	3.6	7.2	10.9	5.2	0.8	0	
[0.21, 0.39]	True DLT rate	0.12	0.30	0.46	0.60	0.70	0.9	
	Selection %	21.2	57.7	19.0	1.7	0.2	0	25.1
	# pts treated	7.4	11.2	5.6	0.9	0.1	0	
[0.21, 0.39]	True DLT rate	0.26	0.50	0.65	0.75	0.80	0.9	
	Selection %	73.1	18.2	0.3	0	0		20.1
	# pts treated	12.4	6.7	0.9	0	0		
[0.21, 0.39]	True DLT rate	0.05	0.10	0.16	0.30	0.50	0.7	
	Selection %	0.2	2.7	23.7	55.7	17.1	0.6	29.2
	# pts treated	3.7	4.7	7.3	9.1	3.9	0.4	
[0.21, 0.39]	True DLT rate	0.02	0.03	0.05	0.12	0.30	0.45	
	Selection %	0	0.1	0.6	19.9	55.7	23.7	29.8
	# pts treated	3.2	3.4	3.8	6.7	8.5	4.3	
[0.21, 0.39]	True DLT rate	0.5	0.65	0.75	0.80	0.90	0.95	
	Selection %	35.8	0.5	0	0	0	0	11.3
	# pts treated	10	1.3	0	0	0		63.7

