### 11.1.3.Sensitivity analysis

To examine the robustness of the proposed BOIN design, we use the BOIN package in R to examine the sensitivity of BOIN design with respect to acceptable toxicity region. The following table shows the simulation results under narrower [0.24, 0.36] or wider toxicity region, while keeping the other simulation parameters unchanged.

We can see that the results are generally similar to those reported in Table 2.

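### Table 2 is offered as the operating characteristics of the proposed design but simulates BOIN alone from level 1 in threes; on nearly all readings the written design treats more patients at overly toxic doses.

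*Combined protocol and SAP*

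**What the plan says.** The Synopsis (Study design) puts the starting dose at 500 mg, "which is at dose level 2 and approximately equal to 1/6 of human equivalent dose". Under ATD phase and cohort size it adds: "The accelerated phase starts with one new patient per cohort". A patient without a first-cycle DLT sends the next patient one level up. The first first-cycle DLT, or the second first-cycle grade 2 or higher toxicity, ends titration. Three new patients are then treated at the current level and BOIN takes over. Section 3.1.1 repeats this but also says that in titration "the newly enrolled patients start at the highest dose level, in which no moderate toxicities are observed in prior patients", which can be read as stricter.

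Section 11.1 describes only the second stage: "We will enroll and treat patients in cohorts of size 3". Section 11.1.2 then says that Table 2 "shows the operating characteristics of the proposed design for this trial with 6 scenarios", while the caption reads "Table 2 Operating Characteristics of the BOIN design". Table 3 is produced "while keeping the other simulation parameters unchanged". The printed R code (appendix section 15.6) sets ten cohorts of three, and its simulation call names neither a titration step nor a starting dose.

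**The concern.** Single-patient escalation from level 2 climbs faster than cohorts of three from level 1, so it can be expected to put more patients on high doses before the interval rules take hold. Table 2 is the only place where an ethics committee or safety reviewer can see how many patients this first-in-human trial expects to treat above the target toxicity rate. If the table belongs to a slower design, those counts, the expected number of DLTs and the total enrolment are wrong for this trial, and the exposure figures err in the reassuring direction.

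**Working it through.** **Inputs from the documents.** Target 0.30; boundaries 0.21 and 0.39; maximum 30 patients; stop at 15 on one dose; isotonic MTD selection; the six sets of true DLT rates in Table 2.

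**BOIN boundaries.** Escalate at or below ln(0.79/0.70) / ln[(0.30×0.79)/(0.21×0.70)] = 0.1210/0.4776 = 0.2532. De-escalate at or above ln(0.70/0.61) / ln[(0.39×0.70)/(0.30×0.61)] = 0.1376/0.4000 = 0.3441. These give every escalate and de-escalate entry of Table 1.

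**Reproducing Table 2.** BOIN from level 1, cohorts of three, no titration:

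| Quantity | Table 2 | Recomputed |
|---|---|---|
| Total patients, S1–S6 | 27.7/25.1/20.1/29.2/29.8/11.3 | 27.9/25.2/20.1/29.1/29.8/11.3 |
| S5 patients by level | 3.2/3.4/3.8/6.7/8.5/4.3 | 3.2/3.3/3.8/6.8/8.5/4.2 |
| S1 correct selection | 58.5% | 59.1% |

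With 1000 simulations the standard error of 58.5% is √(0.585×0.415/1000) = 1.6 points, so the agreement is within simulation error.

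**A check by hand.** Scenario 5 has DLT rates of 2% and 3% at levels 1 and 2. A level-1 start in threes must put at least 3 patients at level 1; Table 2 prints 3.2. In the written design with the DLT trigger only, level 1 is reached mainly if the first patient has a DLT (0.03) and so does at least one of the next three (1 − 0.97³ = 0.087). That gives 0.03 × 0.087 × 3 ≈ 0.01 patients. Level 2 receives about 1 + 0.03 × 3 ≈ 1.1, against 3.4 printed. Simulation also gives about 0.01 and 1.1.

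**Written design.** Mean patients at doses with true DLT rate above 0.39. The Table 2 row adds its printed counts (S1: 5.2 + 0.8 + 0 = 6.0; S3: 6.7 + 0.9 = 7.6). The other rows use 20,000 simulated trials per scenario (10,000 for step-down), with standard errors of at most about 0.1. Percentages are the assumed chance that a patient without a DLT has a grade 2 or higher toxicity.

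| Setting | S1 | S2 | S3 | S4 | S5 | S6 |
|---|---|---|---|---|---|---|
| Table 2 | 6.0 | 6.6 | 7.6 | 4.3 | 4.3 | 11.3 |
| Both triggers, 0% (DLT trigger only) | 10.8 | 11.4 | 12.6 | 8.0 | 7.7 | 17.0 |
| Both triggers, 30% | 10.3 | 11.1 | 12.5 | 7.4 | 7.0 | 16.9 |
| Both triggers, 100% | 7.6 | 9.6 | 11.9 | 5.3 | 5.4 | 16.8 |
| First moderate toxicity ends titration, 30% | 8.8 | 9.8 | 11.9 | 6.2 | 5.9 | 16.6 |
| First moderate toxicity ends titration, 100% | 6.8 | 7.7 | 10.5 | 4.9 | 4.9 | 15.5 |
| Next patient steps down a level, 50% | 7.2 | 8.3 | 10.4 | 4.8 | 4.5 | 15.6 |
| Next patient steps down a level, 100% | 6.2 | 7.2 | 9.1 | 4.2 | 3.8 | 14.5 |

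Independently written code gave 10.3/11.2/12.8/7.2/6.8/17.1 for both triggers at 30% and 7.7/9.9/12.1/5.4/5.4/16.7 at 100%, so those rows agree to within about 0.3.

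**Expected DLTs** (sum over doses of patients × DLT rate; for S1 in Table 2, 0.18 + 0.72 + 3.27 + 2.34 + 0.48 = 7.0):

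| Setting | S1 | S2 | S3 | S4 | S5 | S6 |
|---|---|---|---|---|---|---|
| Table 2 | 7.0 | 7.4 | 7.2 | 6.8 | 5.6 | 5.8 |
| Both triggers, 0% | 9.2 | 9.5 | 10.0 | 8.7 | 7.4 | 9.8 |
| Both triggers, 100% | 7.8 | 8.7 | 9.6 | 7.5 | 6.6 | 9.5 |
| Step-down, 100% | 7.1 | 7.9 | 8.1 | 6.6 | 5.2 | 7.9 |

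**Other rules the documents leave open.** Titration patients are counted in the BOIN tallies because Section 3.1.2 says: "The probability of DLTs is determined by the number of DLTs and the cumulative number of patients treated at the current dose". Decisions at four patients, for which Table 1 has no column, use the same boundaries. Elimination uses a posterior probability of 0.95 with a flat prior, which gives 5 of 9 where Table 1 prints 6 of 9. Alternatives change exposure by −0.1 to +0.6 (6 of 9), −0.6 to +1.6 (titration patients not counted) and −0.7 to +0.2 (filling the switch cohort to three instead of adding three).

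**MTD selection.** Over all readings, correct selection in S1–S5 is 56.2–61.9, 56.6–63.3, 68.0–75.5, 54.6–61.1 and 53.5–59.1%, against 58.5, 57.7, 73.1, 55.7 and 55.7% in Table 2 (level 1, DLT rate 0.26, taken as correct in S3).

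**The case against.** The caption, the Section 11.1 heading, the stated cohort size and the printed code all say BOIN in threes, so the misdescription rests largely on one phrase in Section 11.1.2. Section 11.1.3 introduces Table 3 as BOIN, so that table is incomplete rather than mislabelled. This is fair, but no text says that the tables start at level 1, and the written design has no operating characteristics anywhere else.

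The 0% row is the unfavourable end of the range, and it is implausible where most patients have DLTs. That stands: the 30% and 100% rows are the better guide, and expected DLTs need a range too.

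Titration also brings the benefit it is meant to bring. At the 0% setting, patients at doses with DLT rates below 0.21 fall from 10.8 to 5.4, 15.7 to 8.3 and 17.1 to 8.2 in scenarios 1, 4 and 5, and totals fall to 26.7, 27.1 and 26.7. The drop in low-toxicity exposure is roughly 20 to 50% over the range of assumed rates. This stands and belongs in the replacement tables.

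Titration is not the sole cause. A level-2 start without titration already gives 10.1 and 15.0 patients at toxic doses in scenarios 3 and 6. In scenario 1 it gives only 6.8, and titration at the 30% rate brings this to 10.2.

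**Conclusion.** The concern holds. Tables 2 and 3 describe BOIN alone from level 1, not the trial as written. With both triggers, exposure to doses with DLT rates above 0.39 is about 1.5 to 1.7 times the Table 2 figure at an assumed 30% grade 2 or higher rate (10.3/6.0 in S1, 16.9/11.3 in S6). At 100% it is about 1.2 to 1.6 times (5.3/4.3 in S4, 11.9/7.6 in S3). Scenarios 2, 3 and 6 exceed Table 2 on every reading. The excess vanishes in 4 and 5, and nearly in 1, only if every patient has a grade 2 or higher toxicity and the next patient also steps down.

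The direction is secure; the exact size depends on rules and a toxicity rate that the documents do not settle. Both conclusions of Section 11.1.2 survive in direction: MTD selection stays within about 6 points, and the dose nearest 0.30 still receives the most patients in scenarios 1 to 5. The error lies in toxic exposure, expected DLTs and total enrolment. It should be fixed, but it does not undermine the choice of design.

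**What to change.** Re-run the simulations for the written design: level-2 start, single-patient titration with both triggers, then BOIN in threes. State the assumed grade 2 or higher rate with a range, how titration patients enter the BOIN tallies, and what happens at four patients. The Synopsis and Section 3.1.1 must first be reconciled on what a first moderate toxicity does; this review takes no position on which rule should apply. Replace Tables 2 and 3 and the printed code. Report patients above the MTD, patients at low-toxicity doses, totals and expected DLTs across the assumed range. The cost is a few hours of simulation and two tables with less favourable exposure figures; no dose, decision rule or sample size changes.

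The minimum alternative is one sentence labelling both tables as BOIN alone from level 1 in cohorts of three. That is accurate but leaves the written design without operating characteristics.

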**Table 2 Operating Characteristics of the BOIN design**

Toxicity range	Dose level						Number of pts	% early stopping
	1	2	3	4	5	6		
[0.21, 0.39]	True DLT rate	0.05	0.10	0.30	0.45	0.60	0.8	
	Selection %	0.3	18.9	58.5	20.0	2.3	0	27.7
	# pts treated	3.6	7.2	10.9	5.2	0.8	0	
[0.21, 0.39]	True DLT rate	0.12	0.30	0.46	0.60	0.70	0.9	
	Selection %	21.2	57.7	19.0	1.7	0.2	0	25.1
	# pts treated	7.4	11.2	5.6	0.9	0.1	0	
[0.21, 0.39]	True DLT rate	0.26	0.50	0.65	0.75	0.80	0.9	
	Selection %	73.1	18.2	0.3	0	0		20.1
	# pts treated	12.4	6.7	0.9	0	0		
[0.21, 0.39]	True DLT rate	0.05	0.10	0.16	0.30	0.50	0.7	
	Selection %	0.2	2.7	23.7	55.7	17.1	0.6	29.2
	# pts treated	3.7	4.7	7.3	9.1	3.9	0.4	
[0.21, 0.39]	True DLT rate	0.02	0.03	0.05	0.12	0.30	0.45	
	Selection %	0	0.1	0.6	19.9	55.7	23.7	29.8
	# pts treated	3.2	3.4	3.8	6.7	8.5	4.3	
[0.21, 0.39]	True DLT rate	0.5	0.65	0.75	0.80	0.90	0.95	
	Selection %	35.8	0.5	0	0	0	0	11.3
	# pts treated	10	1.3	0	0	0		63.7

### 11.1.3.Sensitivity analysis

To examine the robustness of the proposed BOIN design, we use the BOIN package in R to examine the sensitivity of BOIN design with respect to acceptable toxicity region. The following table shows the simulation results under narrower [0.24, 0.36] or wider toxicity region, while keeping the other simulation parameters unchanged.

We can see that the results are generally similar to those reported in Table 2.

**Table 3. Sensitivity analysis of BOIN design using scenario 1 in Table 2**

Toxicity range	Dose level						Number of pts	% early stopping
	1	2	3	4	5	6		
[0.18, 0.36]	True DLT rate	0.05	0.10	0.30	0.45	0.60	0.8	
	Selection %	0.6	18.1	56.4	23.2	1.7	0	29.2
	# pts treated	5	10.0	9.8	4.0	0.5	0	
	True DLT rate	0.05	0.10	0.30	0.45	0.6	0.8	

Toxicity range		Dose level						Number of pts	% early stopping
		1	2	3	4	5	6		
[0.18,0.42]	Selection %	0.9	20.5	57.5	19.6	1.5	0	25.1	0.2
	# pts treated	3.7	7.2	10.8	4.8	0.7	0		

## 11.2. Study population

### 11.2.1. All enrolled population

All patients who sign informed consent form will be included. Patient disposition will be tabulated using this data set.

### 11.2.2. All treated population

All patients who receive at least one infusion or any partial dose of Investigation Product. This population will be used for safety analyses and efficacy analyses.

### 11.2.3. Pharmacokinetic data set

All available concentration-time data from patients who receive Investigational Product will be reported. All available PK parameter values will be included in the PK data set and reported, but only patients with adequate PK profiles will be included in the summary statistics and statistical analysis.

### 11.2.4. Response evaluable data set

Response-evaluable patients will be defined as all subjects who receive at least one infusion of Investigational Product, have a baseline tumor assessment with measurable disease, and one of the following: (1) at least one on-treatment tumor evaluation, (2) clinical progression, or (3) death prior to the first one-treatment tumor evaluation.

### 11.2.5. Exploratory pharmacodynamic study

All patients who receive at least one infusion of Investigational Product and have at least one measure of specific marker will be included in the data set for that marker. All treated patients with at least one baseline measurement and at least one on-treatment measurement will be included for the PD assessments.

### **11.3. Statistical considerations**

#### **11.3.1. Demographics and baseline characteristics**

The demographics and baseline characteristics of the patients including age, sex, race, ethnicity, weight, baseline disease diagnosis, and medical conditions will be summarized by dose levels using descriptive statistics.

#### **11.3.2. Extent of exposure**

The dose of Investigational product received by patients will be summarized by dose level. A by-patient listing of treatment exposure will be generated.

#### **11.3.3. Concomitant medications**

Concomitant medications will be coded using the World Health Organization Drug Dictionary (WHODD). Concomitant medications will be summarized. Tabulation will be made with respect to the proportion of subjects taking at least 1 concomitant medication for each preferred term during the study. A listing of concomitant medications by subject will be provided.

#### **11.3.4. Efficacy**

The primary efficacy parameter is the objective response rate: (ORR, number of subjects with confirmed responses of CR or PR), divided by the total number of treated subjects with measurable disease at baseline). Tumor response status will be defined according to RECIST 1.1 (Appendix 15.4). To perform an evaluation of anti-tumor activity, BOR outcomes, ORR, and disease control rate (DCR: number of patients with CR, PR, or SD divided by the total number of treated patients with measurable disease at baseline) will be tabulated by overall frequency distribution. Median time to response and duration of response will be summarized for those subjects with confirmed responses, using Kaplan-Meier methods; PFS will be similarly summarized. Listings of individual tumor measurements, tumor burden and % changes in tumor burden will be provided. Changes in tumor burden will be presented graphically for each disease type, e.g. by waterfall or other plots.

#### **11.3.5. Safety evaluation**

The following safety parameters will be evaluated:

### **11.3.5.1. Adverse events**

An Adverse Event (AE) is defined as any new untoward medical occurrence or worsening of a pre-existing medical condition in a patient or clinical investigation subject administered an investigational (medicinal) product and that does not necessarily have a causal relationship with this treatment. An AE can therefore be any unfavorable and unintended sign (including an abnormal laboratory finding, for example), symptom, or disease temporally associated with the use of investigational product, whether or not considered related to the investigational product. Adverse events can be spontaneously reported or elicited during open-ended questioning, examination, or evaluation of a patient (To prevent reporting bias, patients should not be questioned regarding the specific occurrence of one or more AEs.)

Following the subject's written consent to participate in the study, all SAEs, whether related or not related to study drug, must be collected, including those thought to be associated with protocol-specified procedures. All SAEs must be collected that occur within 70 days of discontinuation of dosing or within 30 days of the last visit for screen failures. The investigator should collect any SAE occurring after these time periods that is believed to be related to study drug or protocol-specified procedure. An SAE report should be completed for any event where doubt exists regarding its status of seriousness. If the investigator believes that an SAE is not related to study drug, but is potentially related to the conditions of the study (such as withdrawal of previous therapy, or a complication of a study procedure), the relationship should be specified in the narrative section of the SAE Report Form.

Adverse events will be coded using the Medical Dictionary for Regulatory Activities (MedDRA) to categorize a system organ class and a preferred term for each adverse event. The number of subjects who experienced at least 1 adverse event, study drug related adverse event, severe (Grade $\geq$  3) adverse event, serious adverse event, and the number of subjects withdrawn due to adverse events will be summarized. For each system organ class and preferred term, summaries will be made with respect to the number and proportion of subjects having at least 1 occurrence of an adverse event during the study, using the worst grade reported within a subject. The incidence of adverse events will be presented overall, by system organ class and preferred term, intensity (based on NCI CTCAE Version 4.0), and additional grouping by severity and relationship to study drug. Individual listings of adverse events will be provided. DLTs and study drug-related Grade  $\geq$  2 adverse events will be listed individually.

